3.2.4 Facility Admission

Facility admission will include any overnight stay in a skilled nursing facility outside of the hospital. Facilities include rehabilitation, subacute rehabilitation and nursing-homes. Generally, such admissions occur as discharges from the hospital setting. Residing at home with a nurse or paid caregiver would not be considered a facility admission. Transfer of care to a rehabilitation center within the same hospital or organization would also be considered a facility admission for

the purpose of the protocol as this implies the subject was not well enough to live independently. The study chairs should be contacted to reconcile ambiguities.

Facility admission will be measured for the prior 3 months at day 100 and day 180 and the prior 6 months at day 365. The cumulative incidence of first admission to a facility as well as the rate of admissions accounting for recurrent admissions will be calculated over one year.

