5.8.4 Admission to a Skilled Nursing Facility

Cumulative incidence of the time to the first facility admission will be described, along with the number of facility admissions per person years of follow up. Time to first admission will be modeled using Cox regression for the cause-specific hazard of admission, in order to compare hazard ratios between CHARM risk groups after adjustment for baseline characteristics. A multivariate proportional rates/means model⁶⁵ for the rate of facility admission accounting for multiple admissions will be estimated after adjustment for baseline characteristics, in order to estimate the relative intensities of facility admissions between the CHARM risk groups

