The following table lists all subject reported assessments to be collected, including the number of items and estimated time to complete at each time point. This appendix also includes all items/questions included on each subject reported assessment. For some assessments, language has been modified to fit administration electronically or on paper, as opposed to in person. Any modifications are noted in the below sections.

| Study Assessments / Testing | # of items | Minutes | Baseline (≤21 days Pre-conditioning) | Day 100 -14/+21 | Day 180 +/- 28 | Day 365 +/- 28 |
|---|------------|---------|--------------------------------------|---------------------|----------------------|----------------------|
| Karnofsky performance status by subject | 1 | <1 | X | X | X | X |
| Facility admissions | 1-3 | 1 | | X | X | X |
| PROMIS Depression | 4-12 | 1-2 | X | X | X | X |
| PROMIS Anxiety | 4-12 | 1-2 | X | X | X | X |
| PROMIS Physical function | 4-12 | 1-2 | X | X | X | X |
| OARS IADL | 6 | 2 | X | X | X | X |
| Falls | 1 | <1 | X | X | X | X |
| Frailty phenotype: Weight loss | 2 | <1 | X | | X | X |
| Frailty phenotype: Exhaustion | 5 | 2 | X | | X | X |
| Frailty phenotype: Activity level | 6-18 | 2-5 | X | | X | X |
| Number of medications for polypharmacy | 4 | 1 | X | | | |
| Race/ethnicity, education, income, demographics | 6 | 2 | X | | | |
| Total time for Subject reported outcomes | | | 13-20 minutes | 7-10 minutes | 11-17 minutes | 11-17 minutes |

Race/ethnicity, education, income, demographics

1. What is the highest grade you finished in school?

- 1-8 grades
- 9-11 grades
- High school graduate
- Some post-college work
- Some college
- Junior college degree
- College degree (BA/BS)
- Advanced degree

2. What is your marital status?

- Single, never married

- Married
- Separated
- Divorced
- Widowed

3. What is your current employment status? (please choose all that apply)

- Employed 32 hours a week or more
- Employed less than 32 hours a week
- Full-time student
- Part-time student
- Homemaker
- On medical leave
- Disabled
- Unemployed
- Retired
- Other

4. What is your race? (please select all that apply)

- White
- Asian
- Black or African-American
- Native Hawaiian or Other Pacific Islander
- Native Indian or Alaskan Native
- Don't know

5. What is your ethnicity?

- Hispanic or Latino
- Not Hispanic or Latino
- Don't know

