 - with some help (*can do light housework but need help with heavy work*); or
 - are you completely unable to do any housework?
6. Can you take your own medicines...
- Without help (*in the right doses at the right time*);
 - With some help (*able to take medicine if someone prepares it for you and/or reminds you to take it*); or
 - Are you completely unable to take your medicines?
7. Can you handle your own money...
- Without help (*write checks, pay bills, etc.*);
 - With some help (*manage day-to-day buying but need help managing your checkbook and paying your bills*); or
 - Are you completely unable to handle money?

Falls in past 6 months

Question has been modified from text box, to multiple choice response in order to control data entry in electronic format.

1. How many times have you fallen in the last 6 months?
- 0 times
 - 1 time
 - 2 times
 - 3 or more times

Facility admissions

At day 100 and 180

1. Have you been admitted to a skilled nursing facility in the last 3 months? This would include an acute rehabilitation facility, nursing-home, or sub-acute rehabilitation. Do NOT include admissions to the hospital.

- Yes
- No
- unsure

At day 365

1. Have you been admitted to a skilled nursing facility in the last 6 months? This would include an acute rehabilitation facility, nursing-home, or sub-acute rehabilitation. Do NOT include admissions to the hospital.

- Yes
- No
- unsure

Frailty phenotype: Weight loss*

Questions have been modified for electronic and paper administration during which patient may not be able to self-weigh or recall exact previous weights. Also modified to remove “Refused” response item, as patients may skip question to refuse.

At Pre-HCT

1. To the best of your knowledge, have you lost or gained weight over the past year?

- Yes
- No
- Don't know

2. [if yes] Did you lose or gain weight because you were trying to, or not (For example, by dieting or exercising)?

- Tried to
- Did not try to
- Don't know

Frailty phenotype: Exhaustion*

Questions have been modified to remove “Refused” response item, as patients may skip question to refuse.

* <https://www.johnshopkinssolutions.com/solution/frailty/>

* <https://www.johnshopkinssolutions.com/solution/frailty/>

1. In the past month, on average have you been feeling unusually tired during the day?

- Yes
- No
- Don't know

2. If yes, have you been feeling unusually tired:

- All of the time
- Most of the time
- Some of the time
- Don't know

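### The facility-admission analyses need dates and counts that the printed survey item does not ask for, and fixed recall periods and unreported time before death leave stays uncounted.

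*Protocol*

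**What the plan says.** Section 5.8.4 of the Protocol sets out four analyses of facility admission:

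- the cumulative incidence of a first admission;
- a regression for it: "Time to first admission will be modeled using Cox regression for the cause-specific hazard of admission";
- a descriptive rate: "along with the number of facility admissions per person years of follow up";
- a proportional rates/means model "for the rate of facility admission accounting for multiple admissions will be estimated after adjustment for baseline characteristics".

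Section 3.2.4 defines the endpoint to match: besides first admission, "the rate of admissions accounting for recurrent admissions will be calculated over one year". It fixes recall at 3 months for the day 100 and day 180 surveys and 6 months for day 365.

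Table 4.2.4 marks facility admissions as subject-reported only. Appendix 4 (Section 6.4) prints one question per survey. At days 100 and 180 it is "Have you been admitted to a skilled nursing facility in the last 3 months"; at day 365 it is "Have you been admitted to a skilled nursing facility in the last 6 months". The answers offered are Yes, No and unsure.

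The appendix describes itself as complete: "This appendix also includes all items/questions included on each subject reported assessment". Yet its own table row reads "Facility admissions | 1-3 | 1", that is, one to three items and one minute.

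**The concern.** A time-to-event model needs an event time, and a recurrent-event model needs every event with its time. The printed item gives neither. A statistical analysis plan can choose how to handle coarse times, but it cannot recover a date or a number that no form asked for.

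Two further weaknesses do not depend on whether sub-items exist. Recall is fixed in calendar length while the survey day may move, so successive periods need not meet. And a subject who dies gives no report for the time since the last survey. CHARM is built to predict non-relapse mortality, so this second loss should fall more heavily on subjects with higher scores.

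At stake is secondary objective 4 (Section 2.2.3). Nursing-home admission is also named in the study hypothesis (Section 2.2.1).

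**Working it through.** The Protocol gives no figure for this endpoint to reproduce. The evaluable sample of 880 is used below only as a denominator. By the plan's formula, 12 x 16 / 0.22 = 872.7, consistent with the stated 880.

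**1. Data needed against data asked**

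- First admission (cumulative incidence, Cox): needs a date. The printed item places a reported stay only somewhere in the prior 3 or 6 months.
- Admissions per person-year and the proportional rates model: need a count, and for the model a time for each stay. The printed item gives at most one Yes per survey, so at most three a year.
- Other sources: the post-transplant registry data named in Sections 2.6.8 and 4.2.2.4 cover GVHD, relapse, toxicity and survival. Facility stays are not named.

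An illustration of the lost counts, using assumed admission rates that are not in the Protocol: with Poisson admissions at rate r per year and survey intervals of 100, 80 and 185 days, the expected number of Yes answers is the sum of 1 - exp(-r x length/365).

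| Assumed rates per year | Expected Yes answers | True ratio | Observed ratio |
|---|---|---|---|
| 0.2 vs 0.4 | 0.193 vs 0.371 | 2.0 | 1.93 |
| 0.5 vs 1.0 | 0.456 vs 0.834 | 2.0 | 1.83 |
| 1.0 vs 2.0 | 0.834 vs 1.414 | 2.0 | 1.70 |

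**2. Recall periods against visit windows**

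Windows are from Table 4.2.1: days 86 to 121, 152 to 208 and 337 to 393. Three months is taken as 91 days and six months as 183.

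- Target days: 100 - 91 = day 9; 180 - 91 = day 89, an 11-day overlap with day 100; 365 - 183 = day 182, a 2-day gap after day 180.
- Largest gaps: surveys at days 86 and 208 give 208 - 91 = 117 and 117 - 86 = 31 days; surveys at days 152 and 393 give 393 - 183 = 210 and 210 - 152 = 58 days.
- Largest overlaps: surveys at days 121 and 152 give 152 - 91 = 61 and 121 - 61 = 60 days; surveys at days 208 and 337 give 337 - 183 = 154 and 208 - 154 = 54 days.
- Latest first survey: 121 - 91 = day 30, so the first 30 days are not asked about.

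**3. Time between the last survey and death**

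Overall survival is from Table 5.9.2, weighted by the evaluable numbers 1617, 1816, 704 and 81 (total 4218).

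- Day 100: (1617 x 88 + 1816 x 87 + 704 x 84 + 81 x 81) / 4218 = 86.8%. Deaths: 880 x 0.1323 = about 116.
- One year: (1617 x 63 + 1816 x 61 + 704 x 57 + 81 x 57) / 4218 = 61.0%. Deaths: 880 x 0.3898 = about 343 (39%).
- With constant hazard from day 0 to 100, survival at day 86 is 0.8677^0.86 = 0.885. So about 880 x 0.115 = 101 of the 116 die before the first survey window opens.
- With constant hazard also from day 100 to 365, survival at day 180 is 78.0%. Of the 227 deaths after day 100, about 77 fall before day 180 and 150 after.
- Days lived in the interval of death by those who die, averaged over all subjects and with surveys on target days: 6.5 + 3.4 + 15.1 = 25.0. Total days lived in the first year: 93.2 + 65.9 + 128.0 = 287.1. The share is 25.0 / 287.1 = 8.7%.

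**The case against.** The strongest reply is that Appendix 4 is not as complete as it says. Weight loss is printed only in its pre-transplant form, and falls only with 6-month recall, although Sections 2.4.8 and 2.6.3 call for other periods at follow-up. The table lists six IADL items and six demographic items where seven of each are printed. For activity level, the table's 6-18 items correspond to six lead questions plus twelve conditional ones. Read the same way, 1-3 facility items could be one lead question and two follow-ups, perhaps the number and date. This stands: a reader might infer that date and count are not collected, but the Protocol shows only that the item list and the printed item disagree.

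A reader might also infer that the planned models cannot be run. That goes too far. Sections 5.8.2 and 5.8.3 already apply cause-specific Cox models to frailty and disability, which are seen only at assessments. First admission could be dated to the survey or treated as interval-censored. A rates model could be fitted to at most three reported events, but it would not measure the number of admissions.

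Three other inferences lack support. Nothing says that subjects who die are entered as dying without an admission. The proportions who die are not the proportion of data lost, since subjects who die after day 100 may have answered earlier surveys. And the 31- and 58-day gaps arise only at opposite window extremes; the reverse extremes give overlaps, in which one stay may be reported twice.

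What remains is the unreconciled item list, recall periods that do not follow the actual survey dates, and the absence of any described proxy or site report for time before death. Section 4.2.5 has vital status checked and the subject then contacted, nothing more.

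**Conclusion.** The point holds for a secondary endpoint; the primary NRM model is unaffected. If the printed item is all that is used, the number of admissions is not measured, and first admission is known only to within 3 or 6 months.

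Whether or not sub-items exist, allowed survey timing can leave up to about 31 and 58 days unasked or cover about 60 and 54 days twice. No report is described for the last stretch before death, which affects about 39% of subjects and about 9% of first-year person-time. That share assumes Table 5.9.2 survival, constant hazard within each period and surveys on target days.

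Under-ascertainment in higher-risk subjects is the expected direction. Its size, and so any weakening of the CHARM association, cannot be derived from the Protocol: admission rates are not given, and double reporting works the other way. The illustrated ratios of 1.93 to 1.70 rest on assumed rates.

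**What to change.** - Reconcile the Appendix 4 table with the printed item. If follow-up items exist, print them.
- Change the recall to 'since your transplant' at the first survey and 'since your last survey' afterwards.
- Confirm or add two sub-items: the number of separate stays, and the month and year of the first.
- Add one line on facility stays since the last survey to the Study Exit Form, which Section 4.2.2.2 already has sites update after a death. It would be completed from information the site already holds.
- For data without dates or counts, analyse first admission as interval-censored between surveys. Censor at the last completed survey rather than assume no admission before death, and report the proportion with any admission per interval in place of a recurrent-admission rate.

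The cost is a revision of the survey and exit form by amendment, with no added visits. Some exit-form answers will be unknown, because sites may not hear of stays elsewhere. Censoring at the last survey may itself be informative and should be stated as a limitation.

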5.8.5 Development of Cognitive Decline

The frequency of cognitive decline will be described by creating a change score from baseline to the day 100 evaluation with a score 2 or less from baseline at day 100 reflecting decline. The effect of CHARM risk groups on cognitive decline will be modeled using logistic regression model.

5.8.6 Health Related Quality of Life

Summary of health-related quality of life measures will be scored according to the recommendations of the developers; of primary interest for this study are the summary measures for depression, anxiety and physical function. For the descriptive analysis only, health-related QOL scores for survivors at specific time points will be summarized using means and standard deviations. Patterns of missing health-related QOL data will be examined using graphical techniques and logistic regression models. At each time point, the effect of baseline covariates including the composite health risk score on the health-related QOL outcomes conditional on being alive at that time point will be estimated using the inverse probability of censoring-weighted generalized estimating equations with independent working correlation model of Kurland and Heagerty.⁶⁴ Subjects who do not complete all baseline assessments will continue to be followed. Therefore, multiple imputation methods may also be used. These methods will provide adjusted comparisons of mean health-related QOL between CHARM risk groups at each time point conditional on being alive at that time point.

5.8.7 Acute GVHD

Incidence of acute GVHD grade II-IV and grade III-IV up to 180 days will be estimated with 95% confidence intervals using the cumulative incidence estimate, treating death prior to acute

GVHD as a competing event. A multivariate Cox regression model for the cause-specific hazard of acute GVHD will be estimated after adjustment for baseline characteristics. The hazard ratios of the CHARM risks groups in predicting acute GVHD will be compared.

5.8.8 Chronic GVHD

Incidence of chronic GVHD up to 1 year will be estimated with 95% confidence intervals using the cumulative incidence estimate, treating death prior to chronic GVHD as a competing event. A multivariate Cox regression model for the cause-specific hazard of chronic GVHD will be developed to estimate hazard ratios of the CHARM risk groups, after adjustment for baseline characteristics.

5.8.9 Serious Organ Toxicities by Day 100

Serious organ toxicities identified for this study (see Table 2.6.9) will be tabulated by type of toxicity. Number of toxicities and number of patients experiencing toxicities will be described for the first 100 days, as well as the cumulative incidence of any serious organ toxicity by day 100, with death as a competing risk. The CHARM risks groups will be compared for their association with incidences of serious organ toxicities.

6 APPENDICES

6.1 APPENDIX 1: HUMAN SUBJECTS

1. Subject Consent

Candidates for the study will be identified as described in Chapter 4 of the protocol. The Principal Investigator or his/her designee at each transplant center will contact the candidates, provide the subject with information about the purpose of the study, and obtain consent. The BMT CTN will provide a template of the consent form to each center. Each center will customize the template according to their local requirements and submit it for review by the local Institutional Review Board (IRB). The DCC will verify the adequacy of the consent forms prior to submission to the IRB. Each center must provide evidence of IRB approval to the DCC.

2. Confidentiality

Confidentiality will be maintained by individual names being masked and assigned a subject identifier code. The code relating the subject's identity with the ID code will be kept separately at the center. The ID code will be generated by and kept on file at the BMT CTN Data and Coordinating Center upon enrollment.

3. Participation of Women and Minorities

Women, ethnic minorities, and other populations will be included in this study. Accrual of women and minorities at each center will be monitored to determine whether their rates of enrollment are reflective of the distribution of potentially eligible women and minorities expected from data reported to the CIBMTR and from published data on incidence of severe aplastic anemia in these groups. Centers will be notified if their rates differ significantly from those expected and asked to develop appropriate recruitment reports.

6.2 APPENDIX 2: HEALTHCARE TEAM ASSESSMENTS

Frailty Assessment

Height and weight measurements

1. Current Height: (measured by study staff or patient self-report at follow-up)
2. Current Weight: (measured by study staff or patient self-report at follow-up)
3. Weight 1 year ago:
 - 3 a. If weight loss in past year: “It seems that you have lost weight over the past year. Did you know that you had lost weight?”
 - Yes
 - No
 - 3 b. If Yes to knowing about weight loss, “Did you lose/gain weight because you were trying to, or not?” (For example, by dieting or exercising)
 - Tried to
 - Did not try to
 - Don’t know
 - Refused

Grip test measurement

1. “Which hand do you use to sign your name?” (This is the Dominant Hand.)
2. “Have you had any recent pain in your hand or wrist or any acute flare-up in your hand or wrist from conditions like arthritis, tendonitis or carpal tunnel syndrome?”
3. “Have you had any surgery on your hands or arms during the last 3 months?”
 - 3 a. If yes, which hand or arm?
4. Was the grip test completed?
 - 4 a. Record Grip Strength measures (kg) – Measurement 1
 - 4 b. Record Grip Strength measures (kg) – Measurement 2
 - 4 c. Record Grip Strength measures (kg) – Measurement 3
5. If no (Grip Test NOT completed), please mark the reason

[figure not shown]
[figure not shown]

[figure not shown]
[figure not shown]
Walking Test Measurement

1. Was the walking test completed?
 - 1 a. Time for first usual pace walk (in seconds):
 - 1 b. Time for second usual pace walk (in seconds):
2. If walking speed test was NOT completed, please mark for the reason:

Montreal Cognitive Assessment (MOCA)

MONTREAL COGNITIVE ASSESSMENT (MOCA)
Version 7.1 Original Version

NAME :
Education : Date of birth :
Sex : DATE :

| VISUOSPATIAL / EXECUTIVE | | | | | | | POINTS |
|---|---|--|---------------|------------------|--------------|--------------|--------------------------------|
|  
[]
 |  
Copy cube
 
[]
 | Draw CLOCK (Ten past eleven) (3 points) | | | | | ___/5 |
| | | [] | [] | [] | [] | [] | |
| | | Contour | Numbers | Hands | | | |
| NAMING | | | | | | | |
|  
[]
 |  
[]
 |  
[]
 | | | | ___/3 | |
| MEMORY | Read list of words, subject must repeat them. Do 2 trials, even if 1st trial is successful. Do a recall after 5 minutes. | FACE | VELVET | CHURCH | DAISY | RED | No points |
| | 1st trial | | | | | | |
| | 2nd trial | | | | | | |
| ATTENTION | Read list of digits (1 digit/ sec.). | Subject has to repeat them in the forward order [] 2 1 8 5 4 | | | | | ___/2 |
| | | Subject has to repeat them in the backward order [] 7 4 2 | | | | | |
| | Read list of letters. The subject must tap with his hand at each letter A. No points if ≥ 2 errors | [] FBACMNAAJKLBAFAKDEAAAJAMOF AAB | | | | | ___/1 |
| | Serial 7 subtraction starting at 100 | [] 93 | [] 86 | [] 79 | [] 72 | [] 65 | ___/3 |
| | | 4 or 5 correct subtractions: 3 pts , 2 or 3 correct: 2 pts , 1 correct: 1 pt , 0 correct: 0 pt | | | | | |
| LANGUAGE | Repeat : I only know that John is the one to help today. [] | | | | | | ___/2 |
| | The cat always hid under the couch when dogs were in the room. [] | | | | | | |
| | Fluency / Name maximum number of words in one minute that begin with the letter F [] ____ (N ≥ 11 words) | | | | | | ___/1 |
| ABSTRACTION | Similarity between e.g. banana - orange = fruit [] train - bicycle [] watch - ruler | | | | | | ___/2 |
| DELAYED RECALL | Has to recall words WITH NO CUE | FACE [] | VELVET [] | CHURCH [] | DAISY [] | RED [] | Points for UNCUEDE recall only |
| | Category cue | | | | | | |
| Optional | Multiple choice cue | | | | | | |
| ORIENTATION | [] Date [] Month [] Year [] Day [] Place [] City | | | | | | ___/6 |
| © Z.Nasreddine MD | | www.mocatest.org | | Normal ≥ 26 / 30 | | TOTAL ___/30 | |
| Administered by: _____ | | Add 1 point if ≤ 12 yr edu | | | | | |

